To achieve the aim of this study we will conduct a randomized controlled trial with three arms during May-Dec 2017. Participants will be Danish adults traveling on vacation in 2018 for a period of 1-3 weeks, recruited from the civil registration system. After enrollment and pretesting, participants will be randomly assigned to one of three experimental conditions. Three experimental groups will receive innovative intervention strategies for promoting sun protection practices during vacation – Protection Routine (1), Protection Routine (2) or both Protection Routine (1+2). The fourth experimental condition will be a minimal treatment control group. The primary outcomes of the trial will be a reduction in frequency of sunburn by adherence to the current sun protection advice from the Danish Cancer Society, i.e., use of shade, hats, protective clothing, and sunscreen as secondary outcomes. We hypothesize that the following two interventions will be able to reduce significantly the UVR exposure and risk of sunburns in Danes going on vacation to destinations with high UVI.

Protection routine 1

The existing evidence of sun protection against the detrimental effect of UV radiation shows that it is effective if performed correctly [26, 28]. We will develop a package of existing training and information and test if it will lead to better adherence. The package will include:

- The rationale of the prioritized sun advice [32]
- Activity planner, with suggestions to why a break from the sun is beneficial and how to plan activities before and after UVI maximum i.e. morning/early noon and afternoon/evening [32]
- Download of the UV-application ‘UVindeks’ for smartphones developed by the campaign and activating UV alert of geographic destination [33]
- A skin type guide

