- A newly developed instruction for correct application of sunscreen [40]

Denmark is not a hat-wearing society. By making smart design hats available and attractive may increase this sun protection behavior, which has large potential in prevention of skin cancer (**ibid: p2**). A very simple study showed that a brief instruction to sunscreen application increased the provided protection significantly [40].

Protection routine 1+2

The group will receive both above mentioned interventions and will reveal potential dose response effects from level of protection.

Control group

All groups including the control group will receive a minimal intervention with the current sun advice from the Danish Sun Safety Campaign.

Study population

The participants of the study are recruited from the Danish civil registration based system. The study population will represent all groups of the Danish population. Eligibility criteria for the project are persons living in Denmark going on vacation in May-December 2018 and having a smartphone compatible with either apple iOS (version 7.0 or newer) or Google Android (version 4.0 or newer). The period May to December is chosen as it includes all types of vacationers. The summer vacation constitutes the majority of the sunny vacations of the Danes. The period includes both the summer, where Danes typically travel to the Mediterranean area and the winter period where travel patterns change a bit to more exotic areas like Thailand, Egypt and the Canarias Islands. Exclusion criteria are persons younger than 18 years of age.

Randomization

The participants will be randomized to one of the intervention groups or to the minimal-treatment control group. The randomization procedure is described in the protocol.

Confounders

Possible confounders includes age, gender, education, skin type, skin cancer history, nevi, sun-seeking behavior and number of sunny vacations in past 5 years [28].

Statistical methods and power calculations

The number of completing participants (n= 1.980) is based on a power calculation, recruitment for similar studies conducted by the applicant [41, 42] and our recent pilot study (unpublished, summarized in the end of this application).

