A statistical power calculation shows that this sample size yields 95 % probability to detect a 10-percentage point drop from 50 % to 40 % in sunburn between an intervention group and the control group, and 80 % probability to detect a 7-percentage point drop from 50 % to 43 %. Our pilot study showed a 17-percentage point difference between our participants (32 %) relative to our annual sun surveys (49%). The number of invited participants to reach a final sample of ~2000 are included in the flow diagram in the protocol.

To obtain the final study sample size, we assumed 25 % of Danes invited to participate will volunteer for the project [41], >80 % will use of interventions (unpublished pilot study) and > 90 % will complete questionnaire [41, 42]. Loss to follow up after one year is expected to be 25 % according to travel patterns with high continuity of the Danes.

Multiple logistic regression analysis will be applied for analysis of differences in sunburn fraction. Analysis of variance will be used to analyze differences in sun protection score and UVR exposure score. Alpha criterion will be p=0.05 (two-tailed).

Intention-to-treat analysis will be applied by using multiple imputation by chained equations to account for missing information on sunburn among non-responders, using PROC MI in SAS 9.3. The imputation procedure includes variables hypothesized to potentially predict missing information (age, sex, education, skin type, sun behaviour, sun protection, sun intentions and intervention group). Analyses will be repeated including responders only and counting non-responders with same sunburn fraction as responders in the control group.

Clustering within families is not included in the planned analysis as it is unlikely to influence the results because participants from the same family have very low odds of being drawn with a total of 30.000 drawn out of the entire Danish population 18+ (app. 4.3 million).

Evaluation by validated questionnaire

Sun protective behavior, exposure to UVR and sunburn will be evaluated by use of a questionnaire validated by personal electronic UV-measurements [7, 43, 44]. This newly developed survey tool has made it possible in this project to evaluate the skin cancer interventions, without tracking of development of skin cancer which can take several years to develop after excessive UVR exposure. The short time period from intervention to evaluation minimizes recall bias.

Success criteria

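### The combined arm is meant to show dose response, but no randomised contrast is specified for it, and power against control is below the stated figures with four equal arms

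*Combined protocol and SAP*

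**What the plan says.** The section *Intervention study* lists "Protection Routine (1), Protection Routine (2) or both Protection Routine (1+2") and a fourth, minimal-treatment control group. *Control group* gives the same basic sun advice to everyone. The four groups are therefore routine 1 (yes/no) by routine 2 (yes/no) on a common background. *Intervention study* also speaks of three arms, and *Main study* of three groups, although each goes on to describe four.

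*Protection routine 1+2* gives the purpose of the combined arm: "The group will receive both above mentioned interventions and will reveal potential dose response effects from level of protection".

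*Statistical methods and power calculations* gives the size: "The number of completing participants (n= 1.980) is based on a power calculation". It states that "this sample size yields 95 % probability to detect a 10-percentage point drop from 50 % to 40 % in sunburn", and "80 % probability to detect a 7-percentage point drop from 50 % to 43" percent for the smaller effect. The comparison is "between an intervention group and the control group", and "Alpha criterion will be p=0.05 (two-tailed"). Sunburn is to be analysed by multiple logistic regression, with no statement of how arm is coded or which contrasts are tested. *Success criteria* compares the intervention groups with control.

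*Completion of intervention* adds an analysis by amount of use.

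**The concern.** One of the four arms is justified by a question that the plan does not say how it will answer. No section names a comparison of 1+2 with a single routine, a trend over 0, 1 and 2 routines, a main effect of a routine, or an interaction. The amount-of-use analysis does not fill the gap: it groups people by what they did after randomisation and is not a randomised comparison.

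Two things are at stake. *Scientific and society perspectives and relevance* says that effective interventions will go into the national campaign, so whether to run one routine or both is a practical question. If the contrast is chosen after the data are seen, the answer carries less weight. Second, the layout allows each routine's effect to be estimated from all participants, whereas a contrast of one arm with control uses half of them. That matters more if the arm-versus-control power is lower than stated.

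**Working it through.** **Inputs.** From *Statistical methods and power calculations*: 1,980 completers, sunburn 50% v 40% and 50% v 43%, two-sided 0.05. Assumption: four equal arms, 1,980/4 = 495 each. The allocation is in a flow diagram that cannot be read here.

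**1. The plan's own figures.** Power = Φ(Δ/SE − 1.96), with SE = √[(p0(1−p0) + p1(1−p1))/n].

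- n = 495, 50% v 40%: SE = √[(0.25 + 0.24)/495] = 0.0315; 0.10/0.0315 − 1.96 = 1.22; power 88.8%.
- n = 495, 50% v 43%: SE = √[(0.25 + 0.2451)/495] = 0.0316; 0.07/0.0316 − 1.96 = 0.25; power 60.0%.
- With pooled variance: 88.7% and 59.8%.
- Three arms of 660: 95.6% and 72.4%. The first stated figure fits; the second does not.
- Unequal allocation: with n0 controls and the rest split equally over three arms, SE = √[0.25/n0 + p1(1−p1)/n1]. For n0 from 400 (n1 = 527) to 660 (n1 = 440), power is 86% to 91% and 56% to 63%.

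With four arms, none of these allocations gives 95% and 80%.

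**2. Marginal effect of a routine.** Average its effect over the other routine: Δ = ½[(p00 − p10) + (p01 − p11)], SE = ½√[Σp(1−p)/495] over the four cells. Let d be the effect of one routine alone and f the share of that effect it adds on top of the other. The 1+2 rate is then 50% − d − fd, and Δ = d(1 + f)/2.

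Example, f = 1 and d = 10 points: cells 50/40/40/30, SE = ½√(0.94/495) = 0.0218; 0.10/0.0218 − 1.96 = 2.63; power 99.6%.

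| Share added (f) | 1+2 rate, d = 10 | Marginal effect (points) | Power | 1+2 rate, d = 7 | Marginal effect (points) | Power |
|---|---|---|---|---|---|---|
| 1 (additive) | 30% | 10.0 | 99.6% | 36% | 7.0 | 88.5% |
| 0.5 | 35% | 7.5 | 92.7% | 39.5% | 5.25 | 65.6% |
| 0.4 | 36% | 7.0 | 88.8% | 40.2% | 4.9 | 59.6% |
| 0.25 | 37.5% | 6.25 | 80.8% | 41.25% | 4.4 | 50.2% |
| 0 (full overlap) | 40% | 5.0 | 61.8% | 43% | 3.5 | 34.8% |
| *One arm v control* | | *10.0* | *88.8%* | | *7.0* | *60.0%* |

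The break-even follows from the standard errors: 0.0220/0.0315 = 0.70, and (1 + f)/2 = 0.70 gives f = 0.40. In information terms, (0.0315/0.0218)² is about 2.1, so the single-arm contrast carries about half the information when effects add.

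**3. Does adding a routine help?** 1+2 against one routine, 495 v 495: about 91% power for 40% v 30% and 62% for 43% v 36%. If only half the effect is added (40% v 35%; 43% v 39.5%), 37% and 20%. A trend over 0, 1 and 2 routines has 99% power at 7 points per step and 89% at 5.

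**4. Interaction.** SE = √[Σp(1−p)/495], twice the marginal SE. Under full overlap: 0.10/0.0443 − 1.96 gives 62%, and 0.07/0.0446 − 1.96 gives 35%. At half-additivity: about 20% and 12%.

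**5. Coding.** In a logistic model with 0/1 indicators and their interaction, the routine 1 coefficient is routine 1 against control: SE = √[1/(495×0.25) + 1/(495×0.24)] = 0.128, the same as pairwise. In cells 50/40/40/30 it falls to 0.093 only when the interaction is left out.

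**The case against.** Arm against control is a legitimate target. The campaign wants to know whether what it delivers works, and a marginal effect averages over receipt of the other routine. The analysis section does not rule out factorial contrasts either. Both points stand, and they are why the pairwise contrasts should stay primary.

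Overlap between the routines is also plausible. All arms get the sun advice, which already covers hat and sunscreen, and routine 1 promotes several protection practices. The 99.6% and 88.5% need sunburn to fall to 30% or 36% in the combined arm. At half-additivity the marginal figures, 92.7% and 65.6%, are still below the stated 95% and 80%.

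Four stronger readings are tempting and are not supported:

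- *The plan excludes factorial analyses.* It leaves coding and contrasts unspecified.
- *It gives up most of its precision.* The loss is about half the information, and only when effects are roughly additive.
- *The margin does worse only if the second routine adds nothing.* It does worse below about 40%.
- *The interaction term answers the dose-response question.* It measures departure from additivity, not whether adding a routine helps, and its test is weak.

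**Conclusion.** The point holds as a gap in specification. The plan states a dose-response purpose for the combined arm and names no randomised contrast that serves it.

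On size: with four equal arms of 495, power against control is about 89% and 60%, where 95% and 80% are stated. Plausible unequal splits over four arms do not change that conclusion. A three-way split would reproduce the 95% but not the 80%, and does not match the four groups described. Marginal effects would be a real gain under near-additivity and a loss under strong overlap. They suit a supporting role and do not by themselves repair the primary power.

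These figures rest on equal allocation (except where a range is shown), a 50% control rate, equal effects of the two routines, and a normal approximation without covariate adjustment. The arm-versus-control comparisons remain valid in themselves.

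**What to change.** 1. State four arms and the allocation consistently. Keep arm against control as the primary contrasts and restate their power for the actual per-arm size.
2. For dose response, pre-specify 1+2 against each single routine, or a trend over 0, 1 and 2 routines. The first is the more direct: a trend can be positive because single routines beat control, even if 1+2 adds nothing to them.
3. As a supporting analysis, report the marginal effect of each routine averaged over the other, by effect coding, marginal standardisation or a model without the interaction. Do not take it from the 0/1-coded coefficients of the interaction model, which are the pairwise contrasts again.
4. Report the interaction estimate with its confidence interval and say that its test is weak (62% and 35% power even under full overlap).

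The cost is a paragraph of text and a few lines of code, with no added participants or questionnaires. The downside is that marginal effects are harder to interpret, and less powerful, if the routines overlap strongly. That is why the pairwise contrasts must stay.

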In the field of skin cancer prevention behavior research Denmark is a leading country together with Australia. Centre for Research Excellence in sun and Health at Queensland University (CRESH) and the Australian SunSmart Campaign are important collaborators [62, 63]. Australian sun behavior is culturally very different from the behavior among northern Europeans. Key players in Denmark, and worldwide are the UVR research group headed by [name] at Bispebjerg Hospital and the Danish Sun Safety Campaign. This project is developing further the clinical research from [name] group [64-67], the population-based research on sun protection in warm-weather resorts [68, 69] and the use of smartphone technology for promoting sun protection [37, 70, 71] by [name] group and the population based intervention efforts of the Danish Sun Safety campaign [8, 10, 29, 72].

Summary of completed pilot studies securing base assumptions

We have previously conducted feasibility and intervention studies demonstrating the feasibility of this study. We have shown a recruitment rate of 25 % when sampled from the Danish civil registration system [41]. We have also shown that the completion rate in this sample among the recruited participants were above 90 % [41, 42].

We have now piloted the preliminary planned interventions in a small study of 147 persons aged 15-65 representing the Danish population in gender, age, education and geography, going on vacation to a country with a higher uv-index (UVI 8+) than Denmark in the summer of 2016 (not published). They were recruited from a web panel during July 2016 and were vacationing for 1-2 weeks in July-mid August. The participants were introduced to the

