May-Dec 2018	Execution of interventions	Adjusting intervention groups according to participation Sending intervention packages for participants Sending questionnaires for post evaluation
Jun 2017 -Feb 2019 Jun - Nov 2019 (follow-up)	Data collection and data handling	Evaluation of participation and possible reminders Conversion of questionnaire data files for SAS and Purification of data Recording of relevant UV Indexes from vacation destinations
May-Dec 2019	1-year Follow-up	Recruitment and scheduling Sending questionnaires for evaluation
May-Aug 2019	Evaluation and documentation	Analysis and manuscript 1 (baseline)
Aug-Nov 2019		Analysis and manuscript 2 (main study)
Dec 2019 - Mar 2020		Analysis and manuscript 3 (follow-up)
Aug 2019 - Sep 2020	Dissemination of results and implementation of successful interventions	Publications in national press and international scientific papers Update of guidelines

Registering trial

The trial will be registered at clinicaltrials.gov.

Civil registry sample

The sample description of the trial to Danish health data board will be developed. Permissions will be gathered from The Danish Data Protection Agency and the National Committee of Health Research Ethics. A sample of 25.400 individuals aged 18 and older will be requested.

Study population recruitment

The study population will be recruited from the Danish Civil Registry System. The aim is to obtain a sample representing all groups of the Danish population. Recruitment for this type of trial is difficult as the target population is not easy to reach without selection bias. To improve recruitment rates invitations will be targeted to the person in the sample or to any family member in the household aged 18 and above. We aim to receive full data for a final population of approximately 2.000 persons.

It may appear, as 8 % of the original draw in the final data is not much; however, as less than half of the Danes are having vacation abroad every year it corresponds to a reach of 18 % among those eligible for the study. Alternative recruitment approaches like airport recruiting most likely would not decrease any bias or yield a higher percentage of recruited travelers. In addition, Danes also departure from nearby airports in Germany and Sweden, which would be difficult to include in the project.

Planned evaluation

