The evaluation will be conducted in the online survey system, SurveyXact, provided by Rambøll. The system is used in numerous evaluations of the Danish Cancer Society. The evaluation is based on the validated UV behavior questionnaire recently developed by Danish Sun Safety Campaign. The questionnaire will be adapted to the trial.

[figure not shown]
Preparation of interventions

An intensive intervention package was developed prior to the study. The package is composed by known elements from the Danish Sun Safety campaign. The package also includes download of the UV-App developed by the Danish Sun Safety Campaign. The app includes an alert function for high UV-Indexes and can be adapted to the correct location by GPS or a selected city around the world. This mobile app is fully developed and available for this trial. The participants randomized to the package will receive alerts to take precautions against solar UVR before and during their vacation.

Invitations

The invitations for the project will be handled (printed, enveloped and sent) by trained volunteers from the Danish Cancer Society. Participants will sign up for the project on a developed web-page of the project. On the project homepage the participants will fill in a short form of contact information, demographic information, departure and arrival dates of their upcoming vacation and baseline sun behavior information for non-responder analyses. Participants who have not yet planned their vacation are instructed to contact the project team

Flow Diagram

once they have planned it. Likewise they will be reminded every 2-3 weeks during the period by mail or phone. Repeated invitations will be sent after two and four weeks to non-responders. Afterwards, participants will be contacted by the volunteers by phone to confirm their participation and receive information about the study. A student will be dedicated in organizing workflow of the volunteers and participate in the training of the volunteers. We have good experiences with this procedure from other projects like www.mituv.dk and www.statusd.dk also funded by TrygFonden.

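### The eligibility criteria omit the sunny, high-UVI destination that defines the trial's question and do not carry over the stated 1-3 week trip, so low-UVI travellers can be randomised.

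*Combined protocol and SAP*

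**What the plan says.** The Study population section is the only place where criteria are labelled as eligibility criteria: "Eligibility criteria for the project are persons living in Denmark going on vacation in May-December 2018 and having a smartphone" running a compatible system. The only exclusion is age: "Exclusion criteria are persons younger than 18 years of age". The same paragraph explains the recruitment window: "The period May to December is chosen as it includes all types of vacationers". It then mentions Mediterranean travel in summer and more distant sunny places in winter, as description and not as a condition.

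Other sections describe a narrower population:

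- The title, the aim and the hypothesis (Intervention study) concern Danes travelling to sunny or high-UVI destinations.
- Intervention study also gives a trip length: "Participants will be Danish adults traveling on vacation in 2018 for a period of 1-3 weeks".
- Study population recruitment equates the eligible with those who travel abroad: "less than half of the Danes are having vacation abroad every year it corresponds to a reach of 18 % among those eligible".
- The pilot, which the success criterion cites as showing that its target is attainable, recruited people "going on vacation to a country with a higher uv-index (UVI 8+) than Denmark in the summer of 2016".

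On screening, the Invitations section says that the sign-up form collects contact and demographic information, plus "departure and arrival dates of their upcoming vacation and baseline sun behavior information for non-responder analyses". Destination is not in that list. A check for a sunny destination is written only in the 1-year-follow-up section. The Time Schedule has destination UV Indexes recorded under data collection and handling, but no planned analysis uses them.

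**The concern.** Staff apply the labelled criteria. Followed literally, those criteria accept an adult smartphone owner whose trip is to a low-UVI place, and no described enrolment step would detect this.

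Two things are at stake. The first is interpretation: the result would be reported for high-UVI vacationers but estimated in a mixture whose composition nobody fixed in advance. The second is power. Part of Protection routine 1 is triggered by UV level (the app alerts when protection is needed at the location), and there may be less sunburn to prevent where UV is low. Including such trips would then pull the arms together.

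The planned adjustment for received UV exposure (Potential bias) cannot recover the intended population. That exposure is measured after randomisation, and the interventions aim to change it.

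**Working it through.** **Inputs from the documents.** 1,980 completers, two-sided alpha 0.05, and sunburn of 50% v 40% between an intervention group and control (Statistical methods and power calculations). Intervention study announces three arms and then describes a fourth condition. Equal allocation gives 1,980/4 = 495 or 1,980/3 = 660 per arm, so both are shown.

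**Assumptions, not in the documents.** A share f of participants is out of scope. Their control-arm sunburn rate is q. For q, 22% is borrowed from the Danish-summer figure for 2014, as an illustration only, and 50% is the case in which the control rate does not change.

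**Formula.** With p̄ = (p1 + p2)/2,

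power = Φ{ [ |p1 − p2|·√n − 1.96·√(2p̄(1 − p̄)) ] / √(p1(1 − p1) + p2(1 − p2)) }.

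**Step 1: the plan's own figures.** The plan states 95% power for 50 v 40% and 80% for 50 v 43%.

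- 495 per arm, 50 v 40%: (0.10 × 22.249 − 1.96 × 0.7036)/0.700 = 1.21, so power is 88.7%. For 50 v 43% it is 59.8%.
- 660 per arm: 95.5% and 72.3%.

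The first stated figure is reproduced with three arms. The second is reproduced with neither arm count. That is a separate matter; here the step only sets the undiluted starting points.

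**Step 2: dilution with no effect in out-of-scope trips.** Control rate = (1 − f) × 0.50 + f × q and intervention rate = (1 − f) × 0.40 + f × q, so the difference is (1 − f) × 10 points whatever q is. Example with f = 0.20 and q = 0.22: 0.444 v 0.364, a difference of 8 points.

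| Out-of-scope share f | Difference | Power, 495 per arm (q = 50% / 22%) | Power, 660 per arm (q = 50% / 22%) |
|---|---|---|---|
| 0 | 10 points | 88.7% | 95.5% |
| 10% | 9 points | 81.2% / 81.8% | 90.8% / 91.2% |
| 20% | 8 points | 71.5% / 72.8% | 83.1% / 84.3% |
| 30% | 7 points | 59.8% / 62.1% | 72.3% / 74.5% |

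**Step 3: the interventions also work at low UVI.** Take the same relative reduction everywhere (40/50 = 0.8) and q = 22%. At f = 0.20 the control rate is 0.444, the intervention rate 0.8 × 0.444 = 0.355, and the difference 8.9 points. Power is 81.5% with 495 per arm and 91.0% with 660. The loss remains but is roughly half as large or less.

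**Step 4: what the recruitment arithmetic assumes.** 8% of the draw is said to equal 18% of the eligible, so the eligible share is 8/18 = 44%. That fits a restriction to travel abroad. The labelled criteria contain no such restriction, and the arithmetic does not include a UVI threshold either.

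**The case against.** The plan as a whole leaves little doubt about whom it wants. The destination is in the title, aim and hypothesis, and a trip length is given. A reader might infer from the labelled criteria that the plan has no trip length, or that it accepts weekend trips and summer-house stays in Denmark. Neither inference holds once Intervention study (1-3 weeks) and Study population recruitment (travel abroad) are read alongside. The gap is that these limits are not carried into the criteria.

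A screen may also exist. The flow diagram is not reproduced, the form is described only briefly, and a phone call follows sign-up. The follow-up procedure, which includes a sunny-destination check, is called similar to the initial one. Destination must be learned at some point, because its UVI is to be recorded. All of this is fair, but none of it states a screen at enrolment, and the labelled criteria would still have to agree with one.

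The out-of-scope share may be small. The background section says that almost half of Danes visit a sunny destination each year, and the recruitment section says that under half travel abroad, so the planners seem to treat the two groups as nearly the same. Nor is zero effect at low UVI established: sunburn in 2014 was 22% in the Danish summer and 27% on sunny vacations, although those figures cover different exposure periods. These points stand, and they make the table in step 2 a pessimistic illustration and not a forecast.

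**Conclusion.** The concern holds in a limited form. The labelled criteria and the described sign-up form contain no sunny or high-UVI condition, so people outside the trial's question can be randomised. The 1-3 week length and the travel abroad are stated elsewhere and need reconciling with the criteria.

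The consequence is a possible mismatch between the enrolled and the intended population, with some loss of power. It is not bias between arms: randomisation protects the comparison for whoever is enrolled. The direction of the power loss was the same in every scenario computed, but its size cannot be stated, because the documents give neither the out-of-scope share nor the effect in such trips. A reader might take the fall to 60% (495 per arm) or 72% (660 per arm) as the expected result. It is not: it needs a 30% share and no effect at all in that share.

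A reader might also infer that the pilot's UVI 8+ is the threshold the trial should have used. The documents do not support that. The pilot covered July to mid-August, whereas this trial deliberately includes winter trips.

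**What to change.** 1. Reconcile the sections Study population, Intervention study and Study population recruitment. State in the eligibility criteria a trip of 1-3 weeks to a sunny, high-UVI destination. The sponsor should set the threshold for the whole May-December window; the pilot's UVI 8+ is a precedent, not a requirement.
2. Add planned destination to the sign-up form and check it before randomisation.
3. Prespecify planned-destination UVI as a covariate in the primary logistic regression. The schedule already provides for recording destination UVI. The value used should be for the destination as planned before randomisation. The covariate does not undo dilution, but it uses a baseline predictor of sunburn.
4. If enrolment has begun, as the July 2018 document date and the April-May recruitment slot suggest, also prespecify an analysis restricted to participants whose destination, as planned before randomisation, was high-UVI.

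The cost is one line in the criteria, one field on the form and one model term. Some sign-ups will be screened out. How many depends on the threshold, and the 18% reach figure covers only travel abroad, so the number to invite should be checked again once the threshold is set.

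### Trip dates and destination UV index are gathered, but no trip variable is named for the sunburn model, the imputation or the strata, giving up a modest amount of power

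*Combined protocol and SAP*

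**What the plan says.** All references are to the combined protocol and SAP.

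- **Pooling.** *Intervention study* sets trip length at one to three weeks. *Study population* covers May to December, taking in Mediterranean summers and "the winter period where travel patterns change a bit to more exotic areas like Thailand, Egypt and the Canarias Islands". *Vacations to sunny destinations is the most important arena for melanoma intervention* ties UV index to burning: the threshold is passed within 20 minutes at UV 9 and within 15 at UV 11.
- **Data gathered.** Under *Invitations*, the sign-up form takes "departure and arrival dates of their upcoming vacation and baseline sun behavior information for non-responder analyses". The *Time Schedule* lists "Recording of relevant UV Indexes from vacation destinations" under data collection and handling.
- **Covariates.** *Confounders* reads: "Possible confounders includes age, gender, education, skin type, skin cancer history, nevi, sun-seeking behavior and number of sunny vacations in past 5 years". *Statistical methods and power calculations* specifies a multiple logistic regression for sunburn without fixing its covariates. Its imputation list holds age, sex, education, skin type, sun behaviour, protection, intentions and arm.
- **Strata.** *Main study* stratifies by gender, age group and region.
- **UV adjustment.** *Potential bias* mentions only adjustment for the UV exposure participants received, in responder analyses.

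**The concern.** Sunburn is assessed once, after one trip. Trip length is therefore the time at risk, and ambient UV index is the strength of the hazard. Both plausibly predict the outcome, and neither duplicates any of the eight named characteristics.

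A prespecified prognostic covariate adds power and accounts for chance imbalance between arms. It would also help the imputation: sunburn is missing for non-responders, while their dates may already be on file.

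The adjustment mentioned under *Potential bias* is no substitute. Received exposure is measured after the trip and is something the interventions aim to reduce, so conditioning on it could remove part of the effect. Planned length and ambient index do not have that problem if they are fixed before allocation is known.

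**Working it through.** **Inputs from the documents.** "The number of completing participants (n= 1.980) is based on a power calculation"; "Alpha criterion will be p=0.05 (two-tailed"; power stated as "95 % probability to detect a 10-percentage point drop from 50 % to 40 % in sunburn between an intervention group and the control group". The plan's other scenario is 43% sunburn against 50%, for which it states 80% power.

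**Assumptions.** Equal allocation (the flow diagram is not available), the mix of trip lengths, and the strength of the trip effects. The documents give none of these.

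**1. The plan's own power.** For two proportions with n per arm, Δ = p0 − p1 and p̄ their mean:

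power = Φ{[Δ − 1.96√(2p̄(1−p̄)/n)] / √([p0(1−p0) + p1(1−p1)]/n)}

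| n per arm | 50 vs 40% | 50 vs 43% |
|---|---|---|
| 660 (1,980/3) | 95.5% | 72.3% |
| 495 (1,980/4) | 88.7% | 59.8% |

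The 95% is reproduced only with three arms. The 80% is reproduced with neither. *Intervention study* speaks of three arms but describes four conditions. That is a separate matter; 495 per arm is used below because four conditions are described.

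**2. Share of variance from trip length.** Assume a constant daily risk giving 50% over 10 days, so risk over d days is 1 − 0.5^(d/10): 0.384, 0.621 and 0.767 at 7, 14 and 21 days. Assume 50/40/10% of trips have these lengths.

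- Mean = 0.5×0.384 + 0.4×0.621 + 0.1×0.767 = 0.517.
- Between-length variance = 0.5×0.133² + 0.4×0.104² + 0.1×0.250² ≈ 0.0194.
- Share = 0.0194/(0.517×0.483) ≈ 0.078.

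Other mixes and baselines give 0.056 to 0.103. A weaker relation (38/50/62%) gives 0.027. The working range is therefore about 3-10%.

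**3. Value on the risk-difference scale.** With standardisation, effective n per arm ≈ n/(1 − R²). Starting from 495:

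| R² | 50 vs 40% | 50 vs 43% | Equivalent total |
|---|---|---|---|
| 0 | 88.7% | 59.8% | 1,980 |
| 0.05 | 90.2% | 62.0% | 1,980/0.95 = 2,084 |
| 0.10 | 91.6% | 64.4% | 1,980/0.90 = 2,200 |

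At R² = 0.03 the equivalent total is 1,980/0.97 = 2,041, or 61 more completers.

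**4. Value in the planned logistic model.** Simulation with 495 per arm and 1,500 runs per scenario (Monte Carlo error about 1 point), without and then with trip length and UV index:

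| Assumed OR per week / per SD of UV index | R² | 50 vs 40% | 50 vs 43% |
|---|---|---|---|
| 1.2 / 1.2 | 0.01 | 88.7 → 88.7% | 60.6 → 59.7% |
| 1.5 / 1.3 | 0.04 | 90.2 → 90.7% | 61.5 → 61.7% |
| 1.5 / 1.5 | 0.06 | 88.5 → 89.8% | 61.6 → 63.1% |
| 2 / 2 | 0.14 | 88.1 → 91.7% | 59.7 → 65.4% |

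In the last scenario (50 vs 40%) the standard error of the log odds ratio rises from 0.129 to 0.139 while the estimate moves from −0.40 to −0.47. The gain shows as power, not as a narrower interval for the odds ratio.

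**5. Chance imbalance.** Under step 2, trip length has mean 11.2 days and SD 4.64. One standard error of the between-arm difference is 4.64×√(2/495) ≈ 0.3 days. That moves the risk difference by about √(0.078×0.25×2/495) ≈ 0.9 points, against a sampling standard error of √(0.25×2/495) ≈ 3.2 points that already includes it.

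**The case against.** **The plan does not exclude these variables.** A reader might infer that the sunburn model leaves them out. The documents do not support that: the list is of possible confounders, the regression's covariates are never fixed, and the use of the recorded UV indexes is not stated. This stands. What can be said is that the variables are not prespecified, which still matters because covariates chosen after results are seen carry less weight.

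**The size rests on an assumed model.** A constant daily risk makes trip length influential. The protocol cites vacation studies in which every participant burned by objective measurement, and thresholds of 15 to 20 minutes. Both suggest that risk may saturate early. The 3-10% is also a marginal share; the gain beyond skin type and sun-seeking behaviour could be smaller. This stands, and it is why the point is minor.

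**It is not free.** It is tempting to say that everything needed is already collected. Destination is not listed on the sign-up form, UV indexes are recorded later, and some participants plan their trip after signing up, possibly after randomisation. This stands and sets a condition on the fix.

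**Season can already be examined.** A reader might infer that the trial cannot say whether its result holds in both travel seasons. Dates are collected, so the comparison is available, though imprecise for winter because summer makes up most sunny vacations.

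None of this answers the core point: trip variables are gathered, and no stated analysis uses them.

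**Conclusion.** The point holds as a minor matter of efficiency. Trip length, season and destination UV index are absent from every named list of covariates, imputation variables and strata, although the trial takes dates and plans to record the index.

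The tempting stronger claim is that this biases the primary comparison. It does not: randomisation protects the comparison, and the ordinary standard error already allows for chance imbalance in trips.

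The likely cost is 1 to 2 points of power, with about 0 to 6 over the simulated scenarios. The upper end needs odds ratios of 2 for both variables. These figures assume 495 per arm and effect sizes that the documents do not give. Adjustment would not restore the stated power under four equal arms: that would need R² of about 1 − 495/641 = 0.23 for the first figure and 1 − 495/796 = 0.38 for the second.

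**What to change.** - Prespecify planned trip length in days and the ambient UV index for the planned destination and dates as covariates in the sunburn logistic regression. Use season of departure where the index is unavailable.
- Put the same variables in the imputation model.
- Report a standardised risk difference from that model. This matches the percentage-point scale of the power statement and lets the gain appear as a narrower interval.
- Take dates and destination as planned and recorded before the participant learns the allocation. Do not use received exposure or self-reported time outdoors.
- Optionally, add an arm-by-season table labelled descriptive.

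The cost is a few more model terms and a short addition to the analysis text. Destination must also be recorded at sign-up or at the pre-departure contact, before allocation is disclosed, including for participants who plan their trip later.
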